5.8.3. Analysis of Quality of Life Variables

The quality of life of patients will be repeatedly measured by the EORTC QLQ-C30 at the day 1 of each treatment cycle for Groups 1 to 5. The change scores of each component of QLQ-C30 will be summarized descriptively at each post-baseline time point. The summary scores of each component of QLQ C30 will also be graphically depicted by longitudinal plots. Partial missing data in QLQ C30 will be taken care of by the scoring algorithm, no additional imputations will be conducted for missing data.

5.8.4. Analysis of Exploratory Efficacy Variable

ORR according to ¹⁸F-FDG-PET using EORTC criteria will be summarized for Group 4 patients (excluding patients enrolled in Germany) and the corresponding 2-sided 95% exact binomial confidence intervals will be derived using the Clopper-Pearson method.

5.8.5. Subgroup Efficacy Analysis

Subgroup efficacy analyses will be performed based on the following factors, respectively:

- gender (Male, Female)
- age group (<65, ≥65)
- race (White, Non-white)
- geographical region (North American, Europe and Rest of World)
- ECOG (0, 1)
- Prior systemic anticancer therapy (Yes, No)
- Prior radiotherapy (Yes, No)
- For Group 1 and Group 3: Metastatic status (Distant or Nodal only)
- For Group 4 and Group 6: Advanced CSCC type (mCSCC, laCSCC)

However, as such analyses may not have enough power for hypothesis tests, the analysis will be exploratory in nature.

5.9. Analysis of Safety Data

The analysis of safety and tolerance will be performed on the SAF, as defined in Section 3.2.

The safety analysis will be based on the reported AEs and other safety information (clinical laboratory evaluations, vital signs and 12-lead ECG). The analysis will comprise the basis upon which conclusions will be drawn regarding the cemiplimab. The AE of special interest will be determined by the list provided by medical monitors.

Period of observation: The observation period will be divided into three segments: pre-treatment, on-treatment and post-treatment.

- The pretreatment period is defined as the time from signing the ICF to before the first dose of study drug.
- The on-treatment period is defined as the day from the first dose of study drug to 105 days after the last dose of study drug or to follow-up visit, whichever is longer. For patients who started cemiplimab as re-treatment more than 30 days after their last regular cemiplimab treatment, the on-treatment period ends at the earlier day of 105 days after the last regular cemiplimab dose or 1 day before their first dose of cemiplimab re-treatment.
- The post-treatment period is defined as the time starting 1 day after the on-treatment period.

Day 1 is the first day of patient receiving cemiplimab treatment, Day –1 is the day before, and there is no Day 0.

The safety analysis will be concentrated on events that occur during on-treatment period. Events that occur during post-treatment period, or during cemiplimab re-treatment will be listed and summarized if necessary.

The summary of safety results will be presented by group and combined.

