 - i. Concomitant medications should be recorded from the date of informed consent through 30 days after last dose of study drug. Any drug started to treat a study drug-related AE during the follow-up will also be recorded. In addition, any cancer treatments should be recorded from the day of informed consent until 105 days (5 half-lives) after the administration of the last dose of cemiplimab. Any AE assessed as related to study treatment and persisting after 105 days (5 half-lives) post-last dose should be reported until resolution to baseline or grade ≤1.
 - j. Nonserious AE and SAE data will be collected from the day of informed consent until 105 days (5 half-lives) after the last dose of cemiplimab. Any AE assessed as related to study treatment and persisting after 105 days (5 half-lives) post-last dose should be reported until resolution to baseline or grade ≤1.

- k. After treatment and follow-up are completed or patients prematurely discontinue treatment and follow-up, patients will be followed quarterly for survival and tumor treatment status, if available. See Section 6.2.2.
- l. In Groups 1 to 5, patients who do not experience PD will be followed for an additional 1 year with assessments every 4 months. Patients in Group 6 will complete 6 months of follow-up (follow-up Visits 1 to 7 only) and will not go into extended follow-up after the 6-month follow-up is completed.
- m. For Group 6 patients who opt to switch to SC dosing and complete the Schedule of Events in Table 8, the only required follow up visits are Follow up visits 1-4. The last visit for these patients will be follow up 4, which provides sufficient long term safety follow up (> 105 days) after last dose of SC cemiplimab. These patients will not enter survival follow up.
- n. ADA collection at follow up visit 3 is only for Group 6 patients who switch to SC cemiplimab.

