7.2. Recording and Reporting Adverse Events

7.2.1. Adverse Events

The investigator (or designee) will seek information on AEs at each patient contact and record all AEs that occur from the time the informed consent is signed until 105 days (5 half-lives) after the end of study treatment. After informed consent has been obtained but prior to initiation of study treatment, only the following categories of AEs should be reported on the AE electronic CRF:

- SAEs
- Nonserious AEs associated with a protocol-mandated intervention (eg, AEs related to an invasive procedure such as a biopsy)

(Other AEs that occur prior to first treatment should be reported on the medical history CRF.)

All AEs after initiation of study treatment and until 105 days (5 half-lives) after the last study treatment, regardless of relationship to study treatment, will be reported on the AE electronic CRF. Additionally, any SAE or other AE of concern that the investigator believes may be related to study treatment and that occurs later than 105 days (5 half-lives) after last study treatment should be reported.

Information on follow-up for AEs is provided in Section 7.2.6. Laboratory, vital signs, or ECG abnormalities are to be recorded as AEs as outlined in Section 7.2.5.

Group 5 patients and Group 6 patients who opt to receive SC dosing only: any local ISRs will be reported as AEs in the CRF, as appropriate.

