9.5.4.1. Adverse Events

Definitions

For safety variables, 3 observation periods are defined:

- The pretreatment period is defined as the time from signing the ICF to before the first dose of study drug.
- The on-treatment period is defined as the day from first dose of study drug to 105 days after the last dose of study drug or to follow-up visit, whichever is longer.
- The posttreatment period is defined as the time after follow-up visit 1.

Treatment-emergent adverse events (TEAEs) are defined as those not present at baseline or represent the exacerbation of a condition present at baseline during the on-treatment period or within 105 days after the last study dose.

Analysis

All AEs reported in this study will be coded using the Medical Dictionary for Regulatory Activities (MedDRA®).

Summaries of all TEAEs by group will include:

- The number (n) and percentage (%) of patients with at least 1 TEAE by SOC and PT
- TEAEs by severity (NCI-CTCAE, version 4.03 grade), presented by SOC and PT
- TEAEs by outcome
- TEAEs by relationship to experimental treatment (related, not related), presented by SOC and PT

Deaths and other SAEs will be listed and summarized by group.

Events of NCI-CTCAE Grade 3 and Grade 4 severity will be summarized by group.

Treatment-emergent adverse events leading to permanent treatment discontinuation will be listed and summarized by group.

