5.9.1. Adverse Events

The verbatim text, the primary system organ class (SOC), and the preferred term (PT) will be displayed in subject listings. Summaries that include frequencies and proportions of patients reporting AEs will include the SOCs and the PTs.

Definitions:

- Pre-treatment AEs are defined as AEs that developed during the pre-treatment period.
- Treatment-emergent AEs (TEAEs) are defined as AEs that developed or worsened during the on-treatment period and any immune-related AEs that occurs any time after the first dose of cemiplimab.
- Post-treatment AEs are defined as AEs that developed or worsened during the post treatment period and are not considered drug related by the investigator.

The focus of adverse event reporting in the CSR will be on TEAEs. For details on handling missing data and partial dates, see Section 6.

Summaries of AEs will include: TEAEs, Treatment related TEAEs, Serious TEAEs, Treatment-related Serious TEAEs, AESI, immune-related AEs, and infusion related AEs. For TEAEs, the following will be summarized:

- The number and proportions of patients reporting at least 1 TEAE, presented by SOC and PT
- TEAEs by severity (CTCAE, version 4.03 grade), presented by SOC and PT
- TEAEs related to treatment, presented by SOC and PT
- TEAEs occurring in $\geq 5\%$ patients, presented by PT
- TEAEs leading to permanent treatment discontinuation, presented by SOC and PT
- TEAEs leading to death, presented by SOC and PT

For each TEAE summary presented by SOC and PT, the summary table will be sorted by decreasing frequency of SOC and PT. For TEAE summary presented by PT, the summary table will be sorted by decreasing frequency of PT.

The irAEs reported by investigator will be summarized. Additionally, irAEs identified by the sponsor will be summarized. All irAEs occurred during the on-treatment and post-treatment period will be included.

For AE listings, the following variables will be displayed:

- Age/Gender
- Verbatim Term, SOC, PT
- AE start date and end date/ongoing (and corresponding study day)
- AE duration
- Relationship to study drug: unrelated or related
- Seriousness (Serious AE or not)
- National Cancer Institute-Common Terminology Criteria for Adverse Events (NCI CTCAE) grade
- Action taken
- Treatment for AE
- Outcome

Counts will be provided for each patient within each SOC and PT. Percentages will be calculated using the number of patients from the SAF in each group.

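### The on-treatment safety period ends at day 105 or at an unnamed follow-up visit, whichever is later, although all-cause AE recording stops at day 105

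*SAP*

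**What the plan says.** SAP 5.9 starts the on-treatment period at the first dose and ends it at "105 days after the last dose of study drug or to follow-up visit, whichever is longer". The visit has no number, although protocol Table 9 has seven numbered follow-up visits and then extended follow-up. Protocol 9.5.4.1 uses the same end point.

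The documents differ on what comes next. The protocol states: "The posttreatment period is defined as the time after follow-up visit 1". The SAP states: "The post-treatment period is defined as the time starting 1 day after the on-treatment period".

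AE collection follows a fixed rule. Protocol 7.2.1 requires "All AEs after initiation of study treatment and until 105 days (5 half-lives) after the last study treatment, regardless of relationship to study treatment". Beyond that date it asks only for "any SAE or other AE of concern that the investigator believes may be related to study treatment". SAP 4.6.1 repeats both rules, and footnote j of protocol Table 9 gives the same 105-day limit.

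Three further provisions bear on the point:
- SAP 5.9.1 counts as treatment-emergent the events of the on-treatment period and also "any immune-related AEs that occurs any time after the first dose of cemiplimab". It confines post-treatment AEs to events the investigator does not consider drug related.
- SAP 5.9 ends the period at day 105, or the day before retreatment if earlier, for patients retreated more than 30 days after their last regular dose.
- The treatment-emergent definition in protocol 9.5.4.1 itself refers to 105 days after the last dose.

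**The concern.** An analysis window should match the period over which events are collected. Here the window can in principle outlast all-cause collection, and its end depends on a visit that is not identified. Two programmers could code the end date differently and both be faithful to the text.

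SAP 5.9.1 makes treatment-emergent events the focus of AE reporting, and SAP 5.9 presents safety by group and combined. If the window runs past day 105, one on-treatment period holds all events up to that day and only related ones afterwards. Its length would also depend on why the patient stopped treatment and on which group the patient was in.

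**Working it through.** **Inputs**
- Last dose within the cycle (protocol Tables 3 to 7): day 43 of 56 in Groups 1 and 2; day 43 of 63 in Groups 3, 5 and 6 (IV); day 29 of 56 in Group 4.
- Follow-up spacing (Table 9): 28 ± 7 days, first from the last cycle visit and then from visit to visit. I take the last cycle visit to be the end-of-cycle visit.
- Extended follow-up (Table 9): one further year, Groups 1 to 5 only.

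**Formula.** With g = days from last dose to cycle end, Follow-up k falls g + 28k days after the last dose. Extended follow-up ends at g + 196 + 365.

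**Check against the plan's own figure.** 7 × 28 = 196 days, or 6.4 months, against about 6 months stated for follow-up. 196 + 365 = 561 days, or 1.54 years, against about 1.5 years in protocol 3.1.2. The calendar reproduces.

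**Nominal days after the last dose, patients who complete treatment**

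| Group | g | FU1 | FU3 | FU4 | FU7 | End of extended follow-up |
|---|---|---|---|---|---|---|
| 1, 2 | 56 − 43 = 13 | 41 | 97 | 125 | 209 | 574 |
| 3, 5 | 63 − 43 = 20 | 48 | 104 | 132 | 216 | 581 |
| 6 (IV) | 63 − 43 = 20 | 48 | 104 | 132 | 216 | none |
| 4 | 56 − 29 = 27 | 55 | 111 | 139 | 223 | 588 |

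SAP 2.3 also lists day 56 as a Group 4 dosing day, which does not agree with protocol Table 5, and the two need reconciling. With day 56, g = 0 and every Group 4 date falls 27 days earlier; the conclusions below are unaffected.

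Group 6 patients who switch to SC dosing finish at Follow-up 4. With the 12-week cycles of Table 8, that is day (85 − 64) + 112 = 133 for Q3W or (85 − 43) + 112 = 154 for Q6W.

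**Reading A: the visit is Follow-up 1.** Taking the last dose 3 days early and the visit 7 days late, Follow-up 1 falls at most at g + 3 + 35 = 51, 58 or 65 days. Day 105 is always later, so the clause is inert. A possible exception is a patient stopped after an 84-day toxicity delay (protocol 5.3.4). If the 28 ± 7 days run from the end of that delay, Follow-up 1 falls at 84 + 21 = 105 to 84 + 35 = 119 days. On this reading the protocol's two periods overlap by 105 − 41 = 64, 105 − 48 = 57 or 105 − 55 = 50 days. An event on day 80 is in both. The SAP's next-day start has no such overlap.

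**Reading B: the visit is a later one, or the last attended.** The first visit past day 105 is Follow-up 4 (Follow-up 3 in Group 4). The post-dose window reaches day 209 to 223 at Follow-up 7 (209/105 = 2.0 to 223/105 = 2.1 times 105 days). In Groups 1 to 5 it reaches day 574 to 588 at the end of extended follow-up (5.5 to 5.6 times).

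Who gets which window under Reading B:
- Stopped for progression: day 105, because protocol 6.2.2 gives one end-of-study visit at 21 to 42 days.
- Retreated: day 105 or earlier (SAP 5.9).
- Stopped for any other reason, including toxicity, or completed treatment: up to the Table 9 visit chosen.

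**What falls in the extra time.** Unrelated events are not collected after day 105. Immune-related events count as treatment-emergent whatever the window. What remains is related, non-immune events after day 105. When the window has closed, such an event is not treatment-emergent. Nor is it a post-treatment AE under SAP 5.9.1, because that category excludes related events. It has no category.

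**The case against.** The best defence is that the protocol does identify the visit. Its on-treatment sentence is followed by a post-treatment period that starts after Follow-up 1, and no text in either document mentions the last visit or extended follow-up in this context. On that reading the window stays at day 105. This stands as the more natural reading of the protocol, but the SAP dropped the visit number, and a clause that almost never operates should not remain in a definition.

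A reader might infer that the plan sets a window of 7 to 19 months for patients who do well. The documents do not support that. It is one reading of an undefined term; the 19-month end cannot apply to Group 6; and patients who stop for toxicity enter the same visits. A reader might also infer that a related event on day 150 is treatment-emergent in one patient and a post-treatment AE in another. That fails twice: an immune-related event is treatment-emergent in both, and a related event cannot be a post-treatment AE under SAP 5.9.1.

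The ratios above describe only the time after the last dose. Counted from the first dose, the extreme case is milder. In Groups 1 and 2 the last dose is 11 × 56 + 42 = 658 days after the first, giving (658 + 574)/(658 + 105) = 1232/763 = 1.6. In Group 4 it is 5 × 56 + 28 = 308 days, giving (308 + 588)/(308 + 105) = 896/413 = 2.2. Planned treatment already ranges from 48 to 108 weeks, so pooled safety tables have unequal observation time regardless. These points limit the size of the problem but do not remove it.

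**Conclusion.** The definition needs correcting, but the consequence is modest. As worded, the visit clause either does nothing (Follow-up 1) or extends the period into time when only related events are reported, with a length that depends on the reason for stopping (any later visit). The documents do not settle which. The affected events are mainly late, related and non-immune. The documents give no rate for these, and the number is probably small. No efficacy result is involved.

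The case for day 105 comes from the documents themselves: all-cause collection, the protocol's treatment-emergent definition and the SAP's retreatment rule all use it. The dates rest on nominal visit timing, completed treatment and the end-of-cycle visit as the anchor for Follow-up 1. The missing category for late related non-immune events arises whenever the window closes, so it has to be repaired together with the end date.

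**What to change.** 1. In SAP 5.9 and protocol 9.5.4.1, delete the alternative end point at the follow-up visit, so that the on-treatment period ends 105 days after the last dose, or the day before retreatment if earlier.
2. In protocol 9.5.4.1, start the post-treatment period on the next day, as the SAP already does.
3. In SAP 5.9.1, remove from the post-treatment AE definition the condition that the investigator does not consider the event drug related. Related non-immune events after day 105 then have a category; list them separately. Immune-related events stay treatment-emergent at any time, as SAP 5.9.1 now provides.

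The cost is wording in three places and a small programming change, with no new data. SAP section 1 allows revision before database lock. The downside is that a few late related events that a later-visit reading would have put in the treatment-emergent tables appear in a listing instead.

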5.9.1. Adverse Events

The verbatim text, the primary system organ class (SOC), and the preferred term (PT) will be displayed in subject listings. Summaries that include frequencies and proportions of patients reporting AEs will include the SOCs and the PTs.

Definitions:

- Pre-treatment AEs are defined as AEs that developed during the pre-treatment period.
- Treatment-emergent AEs (TEAEs) are defined as AEs that developed or worsened during the on-treatment period and any immune-related AEs that occurs any time after the first dose of cemiplimab.
- Post-treatment AEs are defined as AEs that developed or worsened during the post treatment period and are not considered drug related by the investigator.

The focus of adverse event reporting in the CSR will be on TEAEs. For details on handling missing data and partial dates, see Section 6.

Summaries of AEs will include: TEAEs, Treatment related TEAEs, Serious TEAEs, Treatment-related Serious TEAEs, AESI, immune-related AEs, and infusion related AEs. For TEAEs, the following will be summarized:

- The number and proportions of patients reporting at least 1 TEAE, presented by SOC and PT
- TEAEs by severity (CTCAE, version 4.03 grade), presented by SOC and PT
- TEAEs related to treatment, presented by SOC and PT
- TEAEs occurring in $\geq 5\%$ patients, presented by PT
- TEAEs leading to permanent treatment discontinuation, presented by SOC and PT
- TEAEs leading to death, presented by SOC and PT

For each TEAE summary presented by SOC and PT, the summary table will be sorted by decreasing frequency of SOC and PT. For TEAE summary presented by PT, the summary table will be sorted by decreasing frequency of PT.

The irAEs reported by investigator will be summarized. Additionally, irAEs identified by the sponsor will be summarized. All irAEs occurred during the on-treatment and post-treatment period will be included.

For AE listings, the following variables will be displayed:

- Age/Gender
- Verbatim Term, SOC, PT
- AE start date and end date/ongoing (and corresponding study day)
- AE duration
- Relationship to study drug: unrelated or related
- Seriousness (Serious AE or not)
- National Cancer Institute-Common Terminology Criteria for Adverse Events (NCI CTCAE) grade
- Action taken
- Treatment for AE
- Outcome

Counts will be provided for each patient within each SOC and PT. Percentages will be calculated using the number of patients from the SAF in each group.

For Group 6 patients who opt to switch to SC cemiplimab, AEs that occurred during SC cemiplimab will be summarized separately.

Pre-treatment AEs and post-treatment AEs will be listed separately.

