6.2.2. Follow-up

Patients who discontinue study treatment due to PD should return to the clinic 30 days (range: 21 to 42 days) after the last study treatment to complete the EOS assessments indicated in [Table 4](#) through [Table 9](#). After the EOS visit, patients should be followed for survival status until death, loss to follow-up, or study termination by the sponsor.

For all patients in Group 2, tumor biopsies ([Appendix 5](#)) should be obtained at time of progression, whether progression occurs in cycles 1 through 12 or during follow-up (after cycle 12).

Patients who discontinue study treatment due to reasons other than PD (eg, toxicity, confirmed CR after 48 weeks) should enter the follow-up schedule in [Table 9](#). (Note in clarification: Any patients who completed the posttreatment [Table 9](#) follow-up period of 6 months from previous amendments without disease progression will be asked to remain in follow-up. Such patients will be re-consented and asked to return approximately every 4 months (± 14 days) for 1 additional year to complete the extended follow-up assessments in [Table 9](#).)

For patients in Groups 1 or 2 who complete 12 cycles of treatment or for patients in Groups 3, 4, or 5 who complete 6 cycles of treatment without disease progression and subsequently experience disease progression during the follow-up period in [Table 9](#) without any intervening systemic anticancer therapy, resumption of treatment with cemiplimab 350 mg IV Q3W will be allowed. Prior to resumption of cemiplimab treatment, patients must be re-consented and repeat all screening activities (with the exception of providing new archived pathology material, or research biopsies), and the investigator must confirm that the patient still meets all eligibility criteria (other than the exclusion regarding prior treatment with anti-PD-1). Such patients will resume cemiplimab 350 mg IV Q3W for up to 108 weeks (maximum 12 retreatment cycles). The retreatment visit schedule will follow the study schedule in [Table 4](#). ADA samples will not be collected during retreatment. Patients in Group 5 who enter retreatment will not receive an additional dose of cemiplimab SC. For any patients who enter retreatment, the following are not required during retreatment: PK samples, research blood samples, and research tumor biopsies (exploratory tumor biopsies in Groups 2 and 4). *Note: Patients enrolled in Group 6 are not eligible for retreatment.*

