5.7. Exposure to Investigational Product

Exposure to cemiplimab will be examined for each subject and the following variables will be summarized by group:

- The total number of study doses administered
- The total dosage of cemiplimab administered

- Duration of treatment exposure (in weeks) calculated as the minimum of
 - [date of last dose - date of first dose + 14 days based on Q2 weekly dosing schedule] / 7 for Group 1 and Group 2;
[date of last dose - date of first dose + 21 days based on Q3 weekly dosing schedule] / 7 for Group 3, Group 5, and Group 6;
[date of last dose - date of first dose + 28 days based on Q4 weekly dosing schedule] / 7 for Group 4
 - or
 - [date of clinical data cut-off or date of death - date of first dose + 1] / 7
- The number and percentage of subjects exposed to cemiplimab will be presented by specific time points of interest (eg, . 4, 8, 12, 16, 24, 48, 72, 84, 96) for each group.
- The actual dose intensity (mg/kg/week) = total dose received per kg (mg/kg) / duration of treatment exposure (week) for Group 1 and Group 2;
The actual dose intensity (mg /week) = total dose received (mg) / duration of treatment exposure (week) for Group 3, Group 4, Group 5, and Group 6.
- The relative dose intensity = actual dose intensity / planned dose intensity,
 - Planned dose intensity (mg/kg/week) = planned dose (mg/kg) / 2 for Group 1 and Group 2;
 - Planned dose intensity (mg /week) = planned dose (mg) / 3 for Group 3, Group 5, and Group 6;
 - Planned dose intensity (mg /week) = planned dose (mg) / 4 for Group 4

For patients who also receive cemiplimab as re-treatment which starts more than 30 days after their last regular cemiplimab treatment, the retreatment dose will not be included in summary of on-treatment exposure, instead, they will be listed and summarized if necessary.

For Group 6 patients who opt to switch to SC cemiplimab, cumulative exposure to cemiplimab (IV + SC combined) and exposure to SC or IV alone will be summarized.

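### SAP 5.9.1 leaves the immune-related AE window open through cemiplimab retreatment, in conflict with SAP 5.9 and 5.7, which keep retreatment events and doses apart

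*SAP*

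**What the plan says.** Protocol 6.2.2 covers patients in Groups 1 to 5 who complete planned treatment without progression and then progress in follow-up with no intervening systemic anticancer therapy. For them, "resumption of treatment with cemiplimab 350 mg IV Q3W will be allowed", up to 108 weeks or 12 cycles. Group 6 is not eligible.

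The SAP handles the second course in three places:

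- **SAP 5.7 (exposure).** For retreatment starting more than 30 days after the last regular dose, "the retreatment dose will not be included in summary of on-treatment exposure".
- **SAP 5.9 (observation periods).** Under the same condition, "the on-treatment period ends at the earlier day of 105 days after the last regular cemiplimab dose or 1 day before their first dose" of retreatment. The post-treatment period starts the next day and has no stated end. The section adds: "Events that occur during post-treatment period, or during cemiplimab re-treatment will be listed and summarized if necessary".
- **SAP 5.9.1 (TEAE definition).** TEAEs are "AEs that developed or worsened during the on-treatment period", plus "any immune-related AEs that occurs any time after the first dose of cemiplimab". For the irAE summaries, "All irAEs occurred during the on-treatment and post-treatment period will be included".

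Protocol 9.5.4.1 defines TEAEs as arising "during the on-treatment period or within 105 days after the last study dose". It has no irAE extension and does not mention retreatment. SAP 1.2.4 lists the changes from the protocol's statistical section: three added response endpoints and one ORR sensitivity analysis. It lists nothing on AE definitions.

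**The concern.** SAP 5.7 and 5.9 are built to keep the first course and the retreatment course apart. The irAE clause in 5.9.1 removes that separation for one class of event.

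An irAE during retreatment would then count in the TEAE table, and where applicable in the treatment-related, serious, AESI and irAE tables, for the patient's original group. A non-immune AE on the same day would not. The exposure shown beside those tables would omit the doses being given at the time. Groups 1, 2 and 4 were first treated on other regimens and are retreated with 350 mg Q3W, so their irAE counts would mix regimens. SAP 5.9 also presents safety by group and combined, and Group 6 has no retreatment time to contribute.

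SAP 5.9.1 makes TEAEs the focus of AE reporting in the study report. Two programmers working from 5.9 and from 5.9.1 could produce different main tables.

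**Working it through.** **The stated duration.** Retreatment follows the Group 3 schedule (protocol Table 4), with 63-day (9-week) cycles. Maximum duration = 12 cycles × 9 weeks = 108 weeks, as the protocol says.

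**When the 30-day condition is met.** The first tumor assessment in protocol Table 9 is at Follow-up 2, nominally 28 + 28 = 56 days after the final cycle visit. Re-consent and repeat screening follow. Retreatment will ordinarily start more than 30 days after the last regular dose. Whether it starts before or after day 105, SAP 5.9 then places it outside the on-treatment period.

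**The rules applied to an AE that starts in retreatment week 40:**

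| | SAP 5.9 general rule | SAP 5.9.1 TEAE definition | SAP 5.9.1 irAE tables |
|---|---|---|---|
| Immune-related AE | Listed, summary optional | TEAE, since the clause has no end date | Included, if the post-treatment period runs on through retreatment |
| Non-immune AE | Listed, summary optional | Not a TEAE | Not applicable |

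The doses given that week are outside the exposure summary (5.7). Two smaller consequences follow:

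- SAP 5.9.2 limits the worst-grade and shift laboratory tables to the on-treatment period. An immune hepatitis in retreatment could be a TEAE while its ALT value is absent from those tables.
- SAP 5.9.1 restricts post-treatment AEs to those the investigator considers unrelated to drug. A drug-related, non-immune retreatment AE fits neither definition.

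**Planned dosing time that the irAE clause covers but the exposure summary omits,** for a patient who completes both planned courses:

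- Groups 1 and 2: 108 / (96 + 108) = 108/204 = 53%
- Groups 3 and 5: 108 / (54 + 108) = 108/162 = 67%
- Group 4: 108 / (48 + 108) = 108/156 = 69%

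These are maxima in planned weeks, not effects on any reported figure. AE percentages in SAP 5.9.1 use the number of safety-set patients in each group.

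**Effect on a reported percentage.** The documents give neither the retreated fraction *f* nor the probability *q* of a first irAE during retreatment. The added percentage is *f* × *q*. As an assumption only, take *f* from 5% to 20% and *q* from 10% to 30%:

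- Low: 0.05 × 0.10 = 0.5 percentage points
- High: 0.20 × 0.30 = 6 percentage points

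For Group 2 (78 enrolled), that is 78 × 0.005 = 0.4 to 78 × 0.06 = 4.7 patients.

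**The case against.** **SAP 5.9 already sends retreatment events to listings.** It does, with no exception for irAEs. It also names the post-treatment period and retreatment separately, so the irAE-table sentence in 5.9.1 can be read as not reaching retreatment. This stands to the extent that the SAP does not settle where these events go. A reader might infer that they certainly enter the main tables; the text supports only a conflict. The TEAE clause itself refers to no period, so the conflict remains on either reading.

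**The protocol's 105-day limit.** A reader might infer that protocol 9.5.4.1 shows retreatment irAEs should not be TEAEs. It does not. It counts from the last dose of study drug and has no retreatment exception. Read literally, it makes every retreatment AE treatment-emergent, immune or not. For retreatment events, the SAP's departure from the protocol is the carve-out in 5.9. The irAE extension beyond 105 days is a second, separate departure.

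**irAEs can be late.** SAP 4.6.2 says they can occur several months after the last dose, so an open window has a reason. That stands, and the remedy should keep it up to retreatment. Reporting all retreatment AEs and exposure together with the first course would also be coherent, but it would undo the separation that 5.7 and 5.9 already make.

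**Little harm.** Retreatment has several entry conditions. Planned treatment already differs between groups (96, 54, 48 and 108 weeks), and efficacy is analysed by group. Retreatment data are still listed, and restarts within 30 days are not carved out. All of this stands and limits the weight of the point.

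**Conclusion.** The SAP is internally inconsistent on irAEs during retreatment in Groups 1 to 5. Following 5.9.1 puts second-course irAEs into first-course TEAE tables without the matching non-immune events or exposure. Following 5.9 does not. The choice should be fixed in the text.

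The size is unknown because the number of retreated patients is not given. The 0.5 to 6 percentage points shown above rest on two assumed rates and only illustrate the scale. A reader might also take the planned weeks, for example 204 against 96 in Groups 1 and 2, to mean that irAE rates are inflated two- to three-fold. The documents do not support that. The weeks apply only to a patient who completes both courses, Groups 3 to 5 may in any case continue beyond the planned period (protocol 6.3.6), and the tables report patient percentages rather than person-time rates. The primary endpoint is not affected.

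**What to change.** - **SAP 5.9.1.** For patients whose retreatment starts more than 30 days after the last regular dose, end the irAE clause and the irAE tables on the day before the first retreatment dose. This is the condition already used in 5.7 and 5.9. Keep the open window for late irAEs in all other cases.
- **New table.** Report all retreatment AEs, immune and non-immune, in one separate table. Use retreated patients as the denominator and show retreatment exposure. This also gives a place to drug-related, non-immune retreatment AEs.
- **SAP 1.2.4.** List both departures from protocol 9.5.4.1: the irAE extension beyond 105 days and the retreatment carve-out.

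The cost is one sentence, one table and two list entries. There are two downsides. The main table may show slightly fewer irAEs. A late irAE from the first course that starts after retreatment begins would appear in the retreatment table. All events remain reported.
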